The incidence of proximal humerus fractures continues to increase and is among one of the more common fractures seen in the adult population[1]. Proximal humerus fracture dislocations, however, are less common. Despite the decreased prevalence, fracture dislocations have unique challenges with respect to obtaining an anatomical reduction and more frequently involve an open surgical reduction. In addition, depending on other fracture characteristics, there are various treatment options for the fracture itself. Some surgeons may try to preserve the native anatomy with a fixation construct, while others may opt for an arthroplasty procedure. One of the considerations for joint sparing versus replacement is the viability of the humeral head. Previous literature has examined patterns of proximal humerus fractures and have suggested predictable indicators that may lead to humeral head avascular necrosis (AVN)[2-4]. The study by Hertel et al. (2004) demonstrated various fracture patterns associated with an increased risk of AVN. Fracture dislocations were included in the study, however, specific details regarding direction of dislocation were not included. More recently, a large systematic review by Miltenberg et al. (2022), examined the functional outcomes, rate of revision, and short- and long-term complications for proximal humerus fracture dislocations treated with open reduction internal fixation[5]. While fracture dislocations ultimately lead to increased AVN and revision surgery, further discussion surrounding the direction of dislocation and how it may influence overall outcomes was not addressed.

Study Objectives

Primary Objective

The purpose of this study is to first to examine the rates of humeral head AVN in relation to direction of proximal humerus fracture dislocation.

Radiographic measures:

- Humeral head avascular necrosis – as classified by the Cruess classification system[6]
- Direction of the humeral fracture dislocation – characterized by the direction of humeral head in relation to glenoid. Simple objective measure base on A/P, Lateral, and/or Axillary Views.

Secondary Objectives

Secondarily, this study will address patient reported outcome measures with respect to direction of fracture dislocation.

Patient-reported outcome measures:

- Disabilities of Arm, Shoulder and Hand (DASH)
- Constant Score (CS)

Study Design

The study will be an observational, cohort study. Participants will be pulled from a retrospective cohort of all patients with proximal humerus fracture dislocations who underwent operative fixation at Royal Columbian Hospital between January 2011 – July 2021. They will then be grouped by their dislocation directions to look at the development of AVN. Eligible patients will be given the option to consent to the study. This provisional consent will be obtained over the phone, in the form of a verbal agreement. During this agreement the patient will also receive an appointment time for them to come into the office. If agreeable, patients will be asked to come into the clinic to sign the Informed Consent Form, see their treating surgeon, and complete up-to-date radiographs and patient reported outcome measures (PROMs). These radiographs and PROMs will be used to assess AVN and overall function.

Study Population

Inclusion criteria

- Patients ≥ 18 years of age
- Patients who underwent operative fixation of proximal humerus fracture dislocation at Royal Columbian Hospital between January 2011 – July 2021
- Willing and able to consent and complete patient reported outcome measures
- Willing and able to follow the protocol and attend a follow-up visit
- Able to read and understand English or have an interpreter available

Exclusion Criteria

- Skeletally immature patients
- Patients with pathological fractures
- Patients who have had previous operative fixation of proximal humerus
- Patients treated non-operatively
- Patients presenting outside of the study duration window
- Participants treated by a non-participating surgeon
- Deceased patients
- Patients unable to complete patient reported outcome measures
- Patients declining to come back to the clinic for updated x-rays
- Dementia
- Incarceration

Methods

All patients deemed appropriate for study inclusion will be determined based on review of imaging conducted by an orthopedic attending, fellow, or resident to look for proximal humerus fracture dislocations. Patients eligible for study will be grouped based on direction of dislocation in one of four groups, anterior, posterior, varus and valgus. Both surgical and

immediate postoperative protocols were left to discretion of attending surgeon, at the time of the initial surgery. However, the standard postoperative protocol included an initial follow-up for surgical site assessment and removal of sutures and/or staples. In addition, a period of restricted activity status was also left to discretion of attending surgeon.

Study Visit

Study participants will come back for one visit; this will be an observational visit to see how they are doing now. This exam will be conducted in the clinic at a minimum of 2 years postoperatively. Vascularity of the humeral head and union of the fracture will be assessed on anteroposterior and axial radiographs, while patient reported outcomes will be assessed using Constant and Disabilities of Arm, Shoulder and Hand (DASH) Scores.

The Constant Score (CS) is a 100-point scale (high scores = high level of function) composed of individual parameters looking at pain, activities of daily living (ADL), mobility, and measuring the strength of the affected shoulder.

The DASH is a 30-item questionnaire that looks at the ability of a patient to perform certain upper extremity activities. The DASH score ranges from 0 (no disability) to 100 (most severe disability).

Data Collection

Baseline

- Radiographs
 - Dislocation direction
 - Fracture type
- Patient Demographics (Chart Review)
 - Age
 - Gender
 - American Society of Anaesthesiologists (ASA) Score
 - Medical History
 - Social History
- Injury Characteristics
 - Side of injury
 - Mechanism
 - AO/OTA Classification

Surgical Treatment

- Radiographs
- Surgical Demographics
 - Date of surgery
 - Anaesthesia Type
 - Any Additional Procedures on the Injured Limb

Observational Visit

- Radiographs
 - AP, Lateral, and Axillary views
- Radiographic outcomes

- AVN Evidence
- Follow-up Demographics
 - Follow-up Period
 - Date of Last Follow-up
 - Quality of Reduction
 - Re-operations on the Injured Limb
- Patient reported outcomes (DASH, CS)

Outcomes

Primary Outcome Measure

The primary outcome measure is avascular necrosis of the proximal humerus, based on radiographic criteria. (Cruess Classification)

Secondary Outcome Measure

Patient-reported outcome measures will be collected at the one visit

DASH	Developed to assess single or multiple musculoskeletal disorders affecting the upper limb. The DASH is a very commonly used outcome measure that is fully patient-administered and contains 30-questions designed to quantify physical disability and symptoms in individuals with upper limb disorders.
CS	The constant shoulder score is one of the most commonly used outcome measures to assess shoulder disorders. It combines subjective and objective measurements in the form of: pain, activities of daily living, strength, and range of motion to provide you with a final score out of 100.

Radiographic Parameters

A/P, Lateral, and Axillary views.

Statistics

Sample Size

Out of a possible 70 participants we hope to enrol around 56 (with approximately 14 in each of the 4 dislocation groups). This accounts for 20% of the participants of the total to either choose not to enrol or be unavailable due to their morbidity status.

Data Analysis

As this is an observational study with limited patient population and no specific time points to reference, all participants will have the chance to complete the follow-up visit at their leisure. For this reason, we do not foresee needing to exclude any patients for missed appointments. At

the follow-up visit each participant will be assessed for the presence of AVN in comparison to their dislocation direction. Descriptive statistics will be utilized and reported on and parametric analysis will be completed as appropriate.

Ethical Considerations

Potential Benefits

It is not known whether or not participants will gain any direct benefit from the study. It is possible that participants that come back may still be experiencing some pain or issues in their injured limb and want to see the surgeon to discuss potential management.

It is expected that the results of the study will contribute to the literature of shoulder fracture-dislocations and the development of AVN following this type of injury, and provide a possible indication for a large study in the future.

Potential Risks

As this is an observational cohort study there are no anticipated risks to participating in the study. Treatment has already occurred and all follow-up has been completed as per standard of care procedures. The only additional procedures that participants would need to take part in for the study are additional radiographs and the completion of one visit that includes completing PROMs.

As with all research that includes imaging there is a risk of incidental findings. However, this will be dealt with by the most responsible person, who in this case, will be the surgeon that is seeing the participant and assessing their radiographs.

Along with research there is also a risk of loss of confidentiality. Every possible step will be taken to ensure participant confidentiality.

Data Management

Data will be stored in a password protected excel spreadsheet on the FHA M-Drive. Participants will be de-identified and receive a unique study ID. There will be a separate, password protected excel spreadsheet that will house the participants name and their unique study ID. Only necessary study personnel will have access to it.

Confidentiality

All data will be identified using a unique number and letter system in the form of a participant number. This number (e.g. PHFD-001, PHFD-002, etc) will be the only identifiers used for identifying study participants. Most of the data will be electronic and housed in password protected servers in the FHA network on the remote drive. Any paper copies of the CRFs or consent forms will be kept secure in locked cabinets inside the locked research office. The project manager will authorize personnel to access the data only as necessary.

Withdrawal

As the study consists of one study visit we do not anticipate the need for withdrawal. However, participants may choose to withdraw from the study at any time, without any affect to their care of treatment. Withdrawal will include the option to withdraw and still have their last radiograph assessed for the study, or they can choose to have a complete withdrawal (if they haven't completed the study procedures yet). If the participant has completed the study procedures and they choose to withdraw then a discussion will be had about what will happen to the information about them already collected. Participants have the right to request the destruction of their information collected for the study, or they may choose to leave the study and allow the investigators to keep the information already collected.

If participants choose to have the data collected about them destroyed, this will be respected to the fullest extent possible. However, there may be exceptions where the data is not able to be withdrawn, for example, where the data is no longer identifiable or where the data has been merged with other data. If the participant wishes to request the withdrawal of the data, they should let their surgeon and/or research team know.

Blinding

In order to maintain blinding in the study the initial x-rays, taken when the participant's presented to the emergency department, showing the dislocation direction, will be reviewed and assessed by a qualified individual that didn't perform the surgery. During the one-time follow-up visit the surgeon, who performed the participant's surgery, will assess the x-rays the participant had that day to look for any evidence of AVN. The surgeons will be blinded to the dislocation direction the participant experienced initially.

Ethics

The study protocol, case report forms, questionnaires, and the consent form will be submitted and approved by Fraser Health Research Ethics Board prior to study implementation.

The study will be conducted in accordance with the Tri-Council policy statement: Ethical Conduct for Research Involving Humans, the International Conference on Harmonisation Guidance E6: Good Clinical Practice E6: Consolidated Guidelines, applicable government regulations, and institutional research policies and procedures.

Publication/Presentations

Results from the study will be submitted for publication and presented at national conferences as fellow-ship research to influence future studies.

References

1. Schumaier, A. and B. Grawe, *Proximal Humerus Fractures: Evaluation and Management in the Elderly Patient*. Geriatr Orthop Surg Rehabil, 2018. **9**: p. 2151458517750516.
2. Greiner, S., et al., *Humeral head necrosis rate at mid-term follow-up after open reduction and angular stable plate fixation for proximal humeral fractures*. Injury, 2009. **40**(2): p. 186-91.
3. Hertel, R., et al., *Predictors of humeral head ischemia after intracapsular fracture of the proximal humerus*. J Shoulder Elbow Surg, 2004. **13**(4): p. 427-33.
4. Boesmueller, S., et al., *Risk factors for humeral head necrosis and non-union after plating in proximal humeral fractures*. Injury, 2016. **47**(2): p. 350-5.

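### Completing DASH and Constant is an entry condition for the whole study, although the primary outcome, AVN on radiographs, does not need them

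*Protocol*

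**What the plan says.** The requirement appears twice in the protocol's Study Population section. An inclusion criterion reads "Willing and able to consent and complete patient reported outcome measures", and the exclusion list contains "Patients unable to complete patient reported outcome measures". Neither is limited to a particular analysis, so both govern entry to the study.

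Two neighbouring inclusion lines bear on the point: "Willing and able to follow the protocol and attend a follow-up visit" and "Able to read and understand English or have an interpreter available". Refusal to return for x-rays and dementia have exclusion lines of their own.

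On outcomes, the Primary Outcome Measure section states: "The primary outcome measure is avascular necrosis of the proximal humerus, based on radiographic criteria". The Study Visit section says how this is read: "Vascularity of the humeral head and union of the fracture will be assessed on anteroposterior and axial radiographs". The questionnaires belong to the Secondary Objectives: "Secondarily, this study will address patient reported outcome measures with respect to direction of fracture dislocation".

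The Sample Size section hopes to enrol around 56 of a possible 70, about 14 in each of four direction groups. Its 20% allowance names only declining to enrol and morbidity status.

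**The concern.** Eligibility for the primary outcome depends on instruments used only for the secondary one. A patient who consents and comes in for the films can be classified for AVN whether or not a DASH or Constant score exists. As written, that patient is screened out and the AVN reading is lost. No analysis plan can recover it later, because the patient was never enrolled or filmed.

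The text leaves three possible routes into this group, none of them counted:

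- The inclusion line asks for willingness as well as ability. It therefore also bars a patient who accepts the x-rays but declines the questionnaires.
- The language criterion admits a patient with an interpreter, while the DASH is described as "fully patient-administered and contains 30-questions". The protocol does not say whether a DASH completed through an interpreter counts. It may well count.
- Constant is listed among the patient-reported measures but includes measured strength and range of motion. The protocol does not say whether a patient who cannot perform those parts counts as unable to complete it.

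What is at stake is information on the primary outcome in a closed cohort, where lost patients cannot be replaced.

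**Working it through.** **Does any other provision bring these patients back?** Comparing the sections:

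- Consent, attendance, x-ray refusal, dementia and language each have their own wording. The questionnaire lines are therefore not needed to secure the radiograph. What they add is the removal of patients whose AVN status could have been read.
- The Withdrawal section lets a participant withdraw and still have the last radiograph assessed. That covers people already enrolled, not someone screened out. It does show that the protocol accepts an AVN reading that may come without questionnaires.
- No section enrols a patient for the radiographic outcome alone.

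**The plan's own count.** Inputs from Sample Size: 70 possible, 20% loss, four groups.

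70 × (1 − 0.20) = 56, and 56 / 4 = 14. The stated figures reproduce. This is a feasibility count, not a power calculation.

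**Cost of one loss.** 1/14 = 0.0714, or 7.1% of a direction group.

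**Effect on precision.** The protocol states no AVN rate, so 10%, 25% and 40% are assumed. The approximate 95% half-width is 1.96 × √(p(1 − p)/n).

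Worked example at p = 0.25, n = 14: 1.96 × √(0.1875/14) = 0.2268.

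| Assumed AVN rate | n = 14 (no loss) | n = 13 (one loss) | n = 12 (two losses) |
|---|---|---|---|
| 10% | 15.7 points | 16.3 points | 17.0 points |
| 25% | 22.7 points | 23.5 points | 24.5 points |
| 40% | 25.7 points | 26.6 points | 27.7 points |

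Under this formula the relative widening does not depend on the rate: √(14/13) = 1.038 for one loss (3.8%) and √(14/12) = 1.080 for two (8.0%).

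**If 14 is already net of these exclusions.** The protocol does not say. In that case recovering one patient gives n = 15. At 25% the half-width is 1.96 × √(0.1875/15) = 0.2191, so it falls from 22.7 to 21.9 points. √(14/15) = 0.966, which is 3.4% narrower.

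The normal approximation is rough at these sizes. At 10% and n = 14 the lower limit is 10 − 15.7 = −5.7 points, which is impossible. The table shows the order of magnitude and is not a recommended interval.

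**The case against.** The strongest reply is that the protocol is consistent on this point. It plans one visit that yields both films and questionnaires, and one cohort serving both objectives is a legitimate choice. To be lost only through the questionnaire lines, a patient must consent, have no dementia, have English or an interpreter, be willing to follow the protocol and attend for x-rays, yet not complete DASH or Constant. That patient may not exist. The interpreter route is weak, since the description of the DASH is general and does not forbid help. The 14 is approximate, the AVN rates are assumed, and one loss adds only 0.6 to 0.9 points to half-widths of roughly 16 to 26 points, which would hardly change a descriptive conclusion.

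Most of this stands as a limit on size. The group may be empty, the effect is small, and nothing shows bias between directions. It does not justify the criterion. A single cohort for both objectives is convenient, but it gives the AVN comparison nothing in return for the patients it may discard. The willingness wording also makes the affected group wider than inability alone. The radiograph option on withdrawal does not help someone who was never enrolled.

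**Conclusion.** The concern holds. Questionnaire completion is an entry condition for the whole study, the primary outcome does not use it, and no other provision restores a patient excluded on that ground alone. The harm is lost information on the primary outcome, not demonstrated bias.

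The size is small and possibly nil. Each loss costs about 7% of a planned direction group and widens that group's interval by about 4%. These figures rest on the approximate 14 per group, on assumed AVN rates of 10% to 40%, and on at least one such patient existing, which the protocol neither states nor rules out. The change is worth making because it is cheap and the pool is closed.

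**What to change.** Limit the questionnaire criteria to the DASH and Constant analysis:

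1. Split the inclusion line that joins consent and questionnaires. Keep willingness and ability to consent for the whole study, and move the questionnaire half to the DASH and Constant analysis.
2. Move the matching exclusion line to that analysis too.
3. State that following the protocol, in the next inclusion line, does not require questionnaire completion for the AVN analysis. Otherwise that line could still exclude the same patients.

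Anyone who consents and attends for the study radiographs at 2 years or later then enters the AVN analysis. All other criteria stay as they are.

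The cost is an ethics amendment to the wording of three eligibility lines and a slightly different denominator for AVN than for the questionnaires. No visit, film or procedure is added. If no such patient exists, nothing is gained.

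### Varus and valgus are used as dislocation directions although they do not fit the protocol's own definition of direction, can coexist with anterior or posterior, and have no assignment rule

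*Protocol*

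**What the plan says.** The radiographic measures under Primary Objective state that direction is "characterized by the direction of humeral head in relation to glenoid" and call it a "Simple objective measure base on A/P, Lateral, and/or Axillary Views". The Methods section then has eligible patients "grouped based on direction of dislocation in one of four groups, anterior, posterior, varus and valgus".

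The same exposure recurs through the Protocol:

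- Secondary Objectives: the study addresses "patient reported outcome measures with respect to direction of fracture dislocation".
- Data Collection, Baseline: the exposure is one item, "Dislocation direction". Fracture type and AO/OTA classification are separate items; no varus/valgus alignment item is named.
- Sample Size: the enrolment target assumes "approximately 14 in each of the 4 dislocation groups".
- Data Analysis: each participant is "assessed for the presence of AVN in comparison to their dislocation direction".
- Blinding: the presenting films, "showing the dislocation direction, will be reviewed and assessed by a qualified individual" who did not operate. This says who reads the films but not how to classify them.

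**The concern.** Anterior and posterior say where the head lies relative to the glenoid, which is what the definition asks for. Varus and valgus ordinarily describe how the head is angulated on the shaft in the coronal plane. The Protocol gives these two terms no other meaning. They lie on a different axis, so one shoulder can be, for example, both anterior and in varus. Each patient may have only one label, no precedence is stated, and there is no category for any other direction. Two competent readers could label the same film differently and both comply.

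The label carries the whole study. A patient entered as varus or valgus leaves the anterior or posterior group, and no head-to-glenoid direction is recorded for that patient. The anterior and posterior AVN rates then describe only patients not labelled by angulation, while the varus and valgus groups can pool both directions. The Protocol justifies the study by noting that earlier work did not address direction of dislocation; grouped this way, the study may not isolate direction either.

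This is not detail to be left to a statistical analysis plan. The Protocol itself fixes the groups, and an analysis plan cannot recover a direction that was never recorded without a re-read of the films.

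**Working it through.** **The plan's own figures.** The Sample Size section gives 70 possible participants, a 20% allowance for non-enrolment and four groups.

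- Enrolment: 70 × (1 − 0.20) = 56.
- Per group: 56 / 4 = 14.

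Both reproduce. The equal split is assumed; nothing in the Protocol supports it.

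**Patients without a head-to-glenoid label.** Varus plus valgus on these counts: 2 × 14 = 28, and 28 / 56 = 50%.

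**Effect on a direction's AVN rate.** For one direction, let s be the share of its patients labelled by angulation instead, p_n the AVN risk of those who keep the direction label, and p_a the risk of those moved out.

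- Rate for all patients with that direction: (1 − s)·p_n + s·p_a.
- Rate reported for the group: p_n.
- Shortfall: s·(p_a − p_n).

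The Protocol gives neither AVN rates nor the overlap, so both inputs are assumed over a range:

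| Share moved out (s) | Excess 0 points | 10 points | 20 points | 30 points |
|---|---|---|---|---|
| 50% | 0 | 5 | 10 | 15 |
| 25% | 0 | 2.5 | 5 | 7.5 |
| 10% | 0 | 1 | 2 | 3 |

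**Worked check with assumed rates.** Take 28 anterior patients: 14 with neutral alignment at 20% AVN and 14 angulated at 40%.

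- All anterior patients: (14 × 0.20 + 14 × 0.40) / 28 = 8.4 / 28 = 30%.
- Group labelled anterior, if the 14 angulated patients are filed under varus or valgus: 20%.
- Shortfall: 10 points, matching 0.50 × 20.

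**The case against.** The strongest objection is that the calculation lets angulation override direction, although the Protocol states no precedence. If the head-to-glenoid definition governed, every anteriorly displaced head would be labelled anterior, nobody would be moved out, and the error would be zero. That reading does not fit the rest of the plan. Every eligible patient has a fracture dislocation and so has a head-to-glenoid direction. About 14 varus and 14 valgus patients can arise only if angulation displaces that direction for some of them.

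It can also be said that the definition speaks of the direction of the head, which might mean the way it faces. Even so, the definition refers to the glenoid and not the shaft, and the overlap and the missing rule remain.

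Several points do stand:

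- The 50% rests on the unsupported equal split, and the shares and excess risks are assumed. The figures show a mechanism and its possible range, not a measured bias. If angulated heads had lower AVN risk, the sign would reverse.
- The error is measured against the rate in all patients with a given direction. That follows the stated definition, but it is a choice of target.
- The presenting films exist, so a lost direction could be recovered by re-reading.
- Keeping four groups under a redefined exposure with an explicit assignment rule would also remove the contradiction.
- The study is small and mainly descriptive, with no power claim. That lowers expectations of precision, but described rates still need defined groups.

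**Conclusion.** The concern holds and should be corrected before the films are classified. The Protocol defines its only exposure on one axis and groups patients on two, with single labels and no rule for patients who have both features. On the planned counts half the participants (28 of 56) would have no anterior or posterior label. The resulting error in a direction's AVN rate is 0 to 15 points at a 50% share moved out and 0 to 3 points at a 10% share, for an assumed excess risk of 0 to 30 points. The true overlap and AVN rates are unknown, so the size is uncertain and may be zero. The conclusion rests on the ordinary meaning of varus and valgus, because the Protocol defines neither.

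**What to change.** Record two variables from the presenting films already under review:

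1. **Direction** by head-to-glenoid position: anterior, posterior or other. Use it as the exposure for the AVN, DASH and Constant comparisons. Note which views were available and prefer an axillary or lateral view where one exists, without excluding patients who lack one.
2. **Coronal alignment**: varus, valgus or neutral, reported as a descriptive cross-tabulation against direction and AVN.

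Align the wording of Primary Objective, Methods, Data Collection and Blinding with this. In Sample Size, replace the equal split with expected counts: the number of the 70 candidates in each direction, times 0.8.

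The cost is Protocol and case report form wording, one extra data column and a note of available views. No patient or visit is added or lost. Direction groups will probably be unequal and one may be small. The cross-tabulation will be sparse: 3 × 3 = 9 cells for 56 patients averages about 6 per cell, so it should stay descriptive. No gain in power is claimed.

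### Does relating AVN to dislocation direction alone, with no stated role for fracture type or time since surgery, require a change to the plan?

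*Protocol*

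**What the plan says.** The Primary Objective is to "examine the rates of humeral head AVN in relation to direction of proximal humerus fracture dislocation". Study Design has patients "grouped by their dislocation directions to look at the development of AVN", and Data Analysis says that at the visit "each participant will be assessed for the presence of AVN in comparison to their dislocation direction". Data Analysis then commits to descriptive statistics and to parametric analysis where suitable. It names no covariate and excludes none.

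The background cites an earlier study that "demonstrated various fracture patterns associated with an increased risk of AVN". Data Collection lists fracture type and "AO/OTA Classification" at baseline, "Date of surgery" under Surgical Treatment, and the follow-up period at the Observational Visit. None of these is given a role in the comparison.

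Eligible patients are those who "underwent operative fixation at Royal Columbian Hospital between January 2011 – July 2021". On the single visit, the Study Visit section says: "This exam will be conducted in the clinic at a minimum of 2 years postoperatively". No maximum is given, and Data Analysis lets participants choose when to attend.

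**The concern.** Direction was not assigned, so the direction groups may differ in other causes of AVN. Two routes are plausible on the protocol's own text.

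- **Fracture pattern.** The background names it as a predictor of AVN. If a higher-risk pattern is more common in one direction group, that group's crude rate rises even if direction does nothing.
- **Time since surgery.** The surgery window is about 10.5 years wide and the visit has only a lower limit. If AVN keeps appearing after 2 years and follow-up differs by direction, crude rates differ for that reason too.

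The relevant variables are collected but given no stated role. The protocol hopes that the result might justify a larger study, so a spurious contrast could point that study the wrong way.

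**Working it through.** **1. The plan's own figure.** 70 × (1 − 0.20) = 56, and 56 / 4 = 14 per group. This reproduces. It is a feasibility count: no AVN rate, effect size or power is stated.

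**2. Possible bias from fracture type.** All inputs are assumed, with no true direction effect. Spurious difference = (high-risk share in A − share in B) × (AVN risk in high-risk − risk in low-risk). Standard error (SE) for 14 versus 14 = √[(p₁(1−p₁) + p₂(1−p₂))/14].

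| High-risk share, A vs B | AVN risk, high vs low | Crude AVN, A vs B | Difference (points) | SE (points) |
|---|---|---|---|---|
| 40% vs 40% | 30% vs 15% | 21% vs 21% | 0 | 15.4 |
| 60% vs 40% | 30% vs 15% | 24% vs 21% | 3 | 15.8 |
| 60% vs 40% | 40% vs 10% | 28% vs 22% | 6 | 16.3 |
| 70% vs 40% | 30% vs 15% | 25.5% vs 21% | 4.5 | 15.9 |
| 70% vs 40% | 40% vs 10% | 31% vs 22% | 9 | 16.6 |
| 80% vs 20% | 30% vs 15% | 27% vs 18% | 9 | 15.7 |
| 80% vs 20% | 40% vs 10% | 34% vs 16% | 18 | 16.0 |

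Only the last row exceeds one standard error.

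**3. Possible bias from follow-up.** Assume 20% AVN by 2 years and a constant hazard r per year afterwards: F(t) = 1 − 0.8·exp(−r(t−2)).

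- Mean follow-up 8 versus 6 years: F(8) − F(6) = 0, 2.9 and 6.2 points at r = 0, 0.02 and 0.05.
- Mean follow-up 9 versus 5 years: F(9) − F(5) = 0, 5.8 and 12.5 points.

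If onset stops by 2 years, or follow-up is alike across directions, this bias is zero.

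**4. What adjustment would achieve.** A logistic model with 3 direction terms, a two-level fracture term and a time term has 5 parameters. With AVN between 10% and 50%, it has 56 × 0.1 / 5 = 1.1 to 56 × 0.5 / 5 = 5.6 events per parameter.

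Simulation: four groups of 14, 3000 runs per scenario, Firth regression for both models, no direction effect. In the two-level rows AVN is 40% versus 10% by pattern. One group has the first share and the other three have the second. In the unequal follow-up rows the ranges are 5.5–12.5 versus 2–9 years, with 0.1 log odds per year. RMSE is the root mean squared error of the log odds ratio.

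| Scenario | Mean log OR, crude / adjusted | RMSE, crude / adjusted |
|---|---|---|
| Equal shares | 0.02 / 0.04 | 0.95 / 1.04 |
| 60/40 | 0.32 / 0.00 | 0.95 / 1.01 |
| 70/40 | 0.45 / −0.03 | 1.00 / 0.98 |
| 80/20 | 0.98 / −0.02 | 1.35 / 1.16 |
| Equal shares, unequal follow-up | 0.31 / 0.00 | 0.98 / 1.22 |
| 70/40, unequal follow-up | 0.80 / 0.03 | 1.20 / 1.21 |
| Three risk levels, model separates the top one | 0.59 / 0.12 | 1.03 / 0.99 |
| Three risk levels, model joins the top two | 0.59 / 0.25 | 1.05 / 0.95 |

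The three-level rows use AVN of 10/25/50% and strongly unequal shares (15/40/45 versus 45/40/15). Adjustment removes bias when the model is right, but the lost precision mostly cancels the gain. Total error falls by 14% at 80/20 (1.16/1.35 = 0.86) and by 4% to 10% in the three-level rows. It rises by 9% with equal shares (1.04/0.95) and by 24% when only follow-up differs (1.22/0.98). It changes by no more than 2% in the two 70/40 rows. The time term is the costly part: in a separate run with both imbalances, adjusting for fracture type alone gave RMSE 1.04, against 1.18 with time added.

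**The case for a change.** The best case for a change is that the protocol states its comparison three times with direction as the only exposure. It also criticises earlier work for leaving direction out, so the real interest is what direction adds to fracture pattern, and a crude comparison cannot separate the two. Showing fracture type and time from surgery by direction needs no new data, costs no precision and would reveal whether the groups are alike. Grouping fracture types before outcomes are seen would also prevent a choice driven by the results.

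Much of this is sound practice. A reader of the results will want those tables, and the rates should be read as associations. But the tables fall within the descriptive statistics already promised, from variables already listed for collection. The objective asks for rates in relation to direction and makes no causal claim. Stating an objective with one exposure does not fix the analysis as crude, since the analysis sentence leaves the method open. The point about grouping matters only if an adjusted analysis is run, and such a choice is usual content for a statistical analysis plan. The argument from time is weaker still: no passage says that AVN keeps appearing after 2 years or that follow-up differs by direction.

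**Conclusion.** No change is needed. The observation is accurate: fracture type, AO/OTA class, date of surgery and follow-up period are collected without a stated role, and crude rates in a non-randomised cohort can be confounded. But the protocol states nothing wrong and rules nothing out. What is missing is detail that analysts would sensibly supply.

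The size is unknown and may be zero. Under the assumptions above, the spurious difference runs from 0 to 18 points for fracture type and from 0 to 12.5 points for follow-up, against a standard error of 15.4 to 16.6 points. Adjustment is a trade-off at 56 patients: it helps mainly under strong fracture-type imbalance, and the simulation does not support the time term. Keeping the crude table as the main result is reasonable. This conclusion rests on assumed AVN rates, fracture mixes and hazards, since the protocol gives none.
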